### **9.10 Replacement of Subjects**

Subjects who withdraw or are withdrawn before the first dose of study drug on Day 1 of the Treatment Period may be replaced.

Subjects who withdraw or are withdrawn for nonsafety reasons during the study drug treatment period may be replaced at Vertex's discretion.

## **10 STUDY DRUG INFORMATION AND MANAGEMENT**

During the Run-in Period, study drug refers to ELX/TEZ/IVA and IVA.

During the Treatment Period, study drug refers to VX-121/TEZ/D-IVA and matching placebo, ELX/TEZ/IVA and matching placebo, and IVA and matching placebo.

### **10.1 Preparation and Dispensing**

Study drug may be dispensed only under the supervision of the investigator or an authorized designee and only for administration to the study subjects.

### **10.2 Packaging and Labeling**

Study drug tablets will be supplied in blister cards by Vertex. Study drug labeling will be in compliance with applicable local and national regulations. Additional details about packaging, labeling, and dispensing for study drug will be in the Pharmacy Manual.

### **10.3 Study Drug Supply, Storage, and Handling**

VX-121/TEZ/D-IVA will be supplied as FDC film-coated tablets containing 10 mg VX-121/50 mg TEZ/125 mg D-IVA. Matching VX-121/TEZ/D-IVA placebo tablets will be of similar size and appearance and contain 0 mg VX-121/0 mg TEZ/0 mg D-IVA (Table 10-1).

ELX/TEZ/IVA will be supplied as FDC film-coated tablets containing 100 mg ELX/50 mg TEZ/75 mg IVA. Matching ELX/TEZ/IVA placebo tablets will be of similar size and appearance and contain 0 mg ELX/0 mg TEZ/0 mg IVA (Table 10-1).

IVA will be supplied as a tablet containing 150 mg IVA. Matching IVA placebo tablets will be of similar size and appearance and contain 0 mg IVA (Table 10-1).

Blister cards must be stored under conditions noted in the Pharmacy Manual. The investigator, or an authorized designee (e.g., a licensed pharmacist), will ensure that all investigational product is stored in a secured area, under recommended storage conditions, and in accordance with applicable regulatory requirements. To ensure adequate records, all study drugs will be accounted for via the drug accountability forms as instructed by Vertex.

**Table 10-1 Study Drug; Strength/Dosage Form/Route**

Drug Name, Dosage Form, Route	Strength
VX-121/TEZ/D-IVA, FDC tablet, oral	
VX-121	10 mg
TEZ	50 mg
D-IVA	125 mg
VX-121/TEZ/D-IVA-matching placebo, tablet, oral	0 mg
ELX/TEZ/IVA, FDC tablet, oral	
ELX	100 mg
TEZ	50 mg
IVA	75 mg
ELX/TEZ/IVA-matching placebo, tablet, oral	0 mg
IVA, tablet, oral	150 mg
IVA-matching placebo, tablet, oral	0 mg

D-IVA: deutivacaftor; ELX: elexacaftor; FDC: fixed-dose combination; IVA: ivacaftor; TEZ: tezacaftor

#### **10.4 Drug Accountability**

The pharmacist or designated study site staff will maintain information about the dates and amounts of (1) study drug received; (2) study drug dispensed to the subjects; and (3) study drug returned by the subjects. Subjects will be instructed to return all used and unused materials associated with the study drug to the site. These materials will be retained at the site according to instructions provided by Vertex or its designee. The study monitor will review study drug records and inventory throughout the study.

If a site uses a site-specific drug accountability system and/or process, including processes associated with the destruction of returned materials, the process must be documented and approved by Vertex. Additional details will be provided in the Pharmacy Manual. The study monitor must review the drug accountability documentation on a regular basis. The study monitor will promptly communicate to Vertex any discrepancies he/she is unable to resolve with the site.

#### **10.5 Disposal, Return, or Retention of Unused Drug**

The study site staff or pharmacy personnel will retain all materials returned by the subjects until the study monitor has performed drug accountability. The investigator will ensure that the materials are destroyed in compliance with applicable environmental regulations, institutional policy, and any special instructions provided by Vertex. Destruction will be adequately documented.

The principal investigator (PI), study site staff, including pharmacy personnel will assist Vertex with any recall activities (as applicable) and place impacted investigational medicinal product (IMP) in quarantine when requested.

## **10.6 Compliance**

To ensure treatment compliance, the investigator or designee will supervise all study drug dosing that occurs at the site. At each visit, site personnel will review that the subject is compliant with study drug dosing and remind the subject of study drug dosing requirements. Compliance will also be assessed by ongoing study drug count.

If a subject demonstrates continued noncompliance of study drug dosing despite educational efforts, the investigator should consider discontinuing the subject from the study.

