**Table 3-2 Study VX20-121-102: Run-in Period, Treatment Period, and Safety Follow-up Visit**

Event/Assessment a	Run-in Period		Treatment Period b						ETT Visit c	Safety Follow-up Visit 28 (± 7) Days After the Last Dose of Study Drug (If Applicable) d	Comments
	Day -28 (± 1 Day)	Day -14 (Day -15 to Day -3)	Day 1	Day 15 (± 3 Days)	Weeks 4, 8, 12, 16 (± 5 Days)	Weeks 20, 28, 32, 40, 44, 48 (± 5 Days)	Weeks 24 and 36 (± 5 Days)	Week 52 (± 5 Days)			
Clinic visit	X	X	X	X	X e		X	X	X	X	See Section 9.1.8 for use of remote measures in extenuating circumstances.
Telephone contact						X					Assess the subject’s status, any AEs, concomitant medications, treatments, and procedures.
Inclusion and exclusion criteria review	X										Section 8
Randomization			X								Randomization may occur on either Day -1 or Day 1, after all eligibility criteria are confirmed (Section 9.1.3).
CFQ-R			X		Weeks 8 and 16		Week 24	X	X		Completed before the start of any other assessments on the day of the study visit (Section 11.5.3).

a All assessments will be performed before dosing unless noted otherwise.

b To enter the Treatment Period, conditions for entry must be satisfied (Section 9.1.3).

c If the subject prematurely discontinues study drug treatment, an ETT Visit should be scheduled as soon as possible after the decision to discontinue treatment (Section 9.1.5). Subjects who prematurely discontinue treatment during the Run-in Period will complete an ETT Visit and Safety Follow-up Visit, as applicable. Subjects who prematurely discontinue study drug treatment during the Treatment Period should continue to complete all scheduled study visits for assessments following completion of the ETT Visit (and Safety Follow-up Visit, if applicable).

d The Safety Follow-up Visit is required for all subjects, unless otherwise specified (Section 9.1.4). For subjects who complete an ETT Visit 3 weeks or later following the last dose of study drug, the ETT Visit will replace the Safety Follow-up Visit, and a separate Safety Follow-up Visit will not be required (Section 9.1.5).

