### 9.1.3 Treatment Period

Treatment Period assessments are listed in Table 3-2.

The Treatment Period will be randomized, double-blind, and ELX/TEZ/IVA-controlled. It will last approximately 52 weeks (Day 1 through Week 52). Study drug administration details are provided in Section 9.6.

Randomization will occur before the first dose of study drug during the Treatment Period and may occur on either Day 1 or Day -1. Randomization and stratification details are provided in Section 9.2.

To enter the Treatment Period, subjects must have stable CF disease (as judged by the investigator) and have remained on a stable CF treatment regimen during the Run-in Period. Female subjects also must have a negative pregnancy test at Day 1 before receiving randomized study drug. If these conditions are not met (for example, if the subject has an acute upper or lower respiratory infection, PEx, or changes in therapy [including antibiotics] for sinopulmonary disease within 28 days before the Day 1 Visit [first dose of study drug in the Treatment Period]), the subject is considered a run-in failure and cannot enter the Treatment Period or rescreen.

The Week 12 Visit may be performed either in the clinic or as a home health visit, if permitted by local regulations. All home health visits must have a consultation between the subject and investigator (i.e., in person, phone, or telemedicine video conference). This consultation should occur within 2 business days before or after the home health visit and can be outside the visit window. Additional details regarding home health visits will be provided in the Study Reference Manual.

Subjects who prematurely discontinue study drug treatment will remain in the study from the time of discontinuation of study drug treatment through the last scheduled study visit (Section 9.1.5).

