### **9.1.5 Early Termination of Treatment**

If a subject prematurely discontinues study drug treatment, an Early Termination of Treatment (ETT) Visit should be scheduled as soon as possible after the decision to discontinue treatment. Subjects who prematurely discontinue treatment will also be required to complete the Safety Follow-up Visit, approximately 28 ( $\pm$  7) days after their last dose of study drug.

If the ETT Visit occurs 3 weeks or later following the last dose of study drug, then the ETT Visit will replace the Safety Follow-up Visit, and a separate Safety Follow-up Visit will not be required.

If a subject withdraws consent for the study, no further assessments will be performed. Vertex may retain and continue using the study data and samples after the study ends, and may use the samples and information in the development of the study compound, for other drugs and diagnostics, in publications and presentations, and for education purposes. If a subject withdraws from the study, the study data and samples collected will remain part of the study (Section 9.9).

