#### **9.1.5.2 Discontinuation During the Treatment Period**

Subjects who prematurely discontinue study drug treatment during the Treatment Period should continue to complete all scheduled study visits for assessments following completion of the ETT Visit (and Safety Follow-up Visit, if applicable), as detailed in Table 3-2.

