### 9.9 Removal of Subjects

Subjects may withdraw from the study at any time at their own request. Subjects may be withdrawn from study drug treatment at any time at the discretion of the investigator or Vertex for safety, behavior, noncompliance with study procedures, or administrative reasons. A subject who withdraws from study drug treatment will continue to be followed unless the subject withdraws consent (and assent, as applicable).

In addition, a subject must be discontinued from study drug treatment if the subject meets any of the following criteria:

- Has a screening *CFTR* genotype that does not confirm study eligibility if a previous *CFTR* genotype laboratory report was used to establish eligibility. These subjects must be discontinued from the study (Section 8.1)
- Meets any of the stopping (discontinuation) criteria (Section 9.8)
- Becomes pregnant (Section 11.6.7.2)

Subjects who discontinue study treatment early should continue to return for study assessments, as noted in Section 9.1.5.

If a subject does not return for a scheduled visit, reasonable effort will be made to contact the subject. In any circumstance, reasonable effort will be made to document subject outcome. The investigator will inquire about the reason for withdrawal, request that the subject return all unused investigational product(s), request that the subject return for an ETT Visit and Safety Follow-up Visit, if applicable (see Section 9.1.4), and follow up with the subject regarding any unresolved AEs.

If a subject withdraws consent or assent for the study, no further assessments will be performed. Vertex may retain and continue using the study data and samples after the study ends and may use the samples and information in the development of the study compound, for other drugs and diagnostics, in publications and presentations, and for education purposes. If a subject withdraws from the study, the study data and samples collected will remain part of the study. A subject will not be able to request the withdrawal of his/her information from the study data. A subject may request destruction of the samples collected from him/her during the study as long as those samples can be identified as his/her samples.

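### Protocol 10.6 tells investigators to consider taking persistently dosing-noncompliant subjects out of the study, while the other Treatment Period rules stop drug only and keep all scheduled visits

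*Protocol*

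**What the plan says.** Protocol 10.6 covers continued dosing noncompliance despite educational efforts. In that case, "the investigator should consider discontinuing the subject from the study". It has no cross-reference to the removal or follow-up rules and is not limited to one study period.

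The other sections separate stopping drug from leaving the study:

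- **Protocol 9.9** lets the investigator or sponsor withdraw a subject from study drug treatment "for safety, behavior, noncompliance with study procedures, or administrative reasons". The subject is then followed unless consent or assent is withdrawn. The only involuntary removal from the study itself that 9.9 lists is for a screening genotype that does not confirm eligibility.
- **Protocol 9.1.3**: subjects who stop drug early "will remain in the study from the time of discontinuation of study drug treatment through the last scheduled study visit".
- **Protocol 9.1.5.2**: subjects who stop drug during the Treatment Period "should continue to complete all scheduled study visits for assessments following completion of the ETT Visit". Table 3-2 footnote c repeats this.
- **Protocol 9.1.5** adds that subjects who stop drug early "will also be required to complete the Safety Follow-up Visit". If a subject does not return, 9.9 has the investigator "request that the subject return for an ETT Visit and Safety Follow-up Visit, if applicable".
- **Protocol 9.1.5.1**: subjects who stop drug in the Run-in Period are not randomized and complete only the ETT and Safety Follow-up Visits, as applicable.

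On the analysis side, SAP 8.3.1.2 handles treatment discontinuation before Week 24 by treatment policy, using later ppFEV1 values where they exist. SAP 8.3.2.2 applies the same handling to sweat chloride.

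**The concern.** The primary estimand depends on values collected after drug is stopped, and the follow-up rules are written to collect them. Section 10.6 is where a site would look for guidance on poor dosing adherence, and it points to the wrong action. A site that follows it literally could close out a subject who was still willing to attend.

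The missing values would come from poor adherers, for whom the missing-at-random assumption in SAP 8.3.1.3 is least assured. Protocol 12.3.3.1 defers missing-data sensitivity analyses to the SAP. The only supplementary analysis in SAP 8.3.1.4 is a hypothetical-strategy estimand, analysed with the same model under the same assumption.

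At stake are some Week 16 and Week 24 ppFEV1 and sweat chloride values, and PEx follow-up to Week 52.

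**Working it through.** **Is 10.6 a deliberate exception?** Nothing says so. Section 9.9 uses the two terms distinctly, and SAP 8.2.1 counts treatment discontinuation and study discontinuation separately. A subject removed under 10.6 in the Treatment Period has also stopped study drug, so 9.1.3, 9.1.5.2 and footnote c apply to that subject and conflict with 10.6.

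**The plan's power figure.** Inputs from Protocol 12.1: 200 per arm, 10% drop-out, SD 8, margin 3, true difference 0, 1-sided 0.025.

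- Evaluable per arm = 200 × 0.90 = 180.
- SE = 8 × √(2/180) = 0.843, and 3/0.843 − 1.960 = 1.598, so power is 94.5% (94.4% with the noncentral t). The stated figure of more than 90% is reproduced.
- With an assumed total loss of 15% or 20%, power is 93.2% or 91.7%.
- Sweat chloride (SD 14, difference 5, 2-sided 0.05): 92.3% at 180 per arm, 90.7% at 15% loss and 89.0% at 20% loss. Only a doubling of the planned loss takes it just below 90%.

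**What one removed subject could lose (illustration).** L is the study day of last dose. Scheduled visits up to L are taken as attended on their target days. SAP Table 11-1 assigns efficacy measurements by study day.

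*ppFEV1.* Table 3-2 schedules clinic spirometry at both the ETT and Safety Follow-up Visits. The windows are Week 8 (43, 85], Week 16 (85, 141] and Week 24 (141, 211]. With Safety Follow-up on L + 28:

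| Last dose (L) | Safety Follow-up day | Week 16 | Week 24 |
|---|---|---|---|
| up to 57 | up to 85 | empty | empty |
| 58 to 113 | 86 to 141 | filled | empty |
| 114 or later | 142 or later | filled | filled |

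The allowed ±7 days move the limits 57 and 113 to 64 and 120 (visit at L + 21) or to 50 and 106 (visit at L + 35).

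*Sweat chloride.* Table 3-2 schedules it at the ETT Visit but not at Safety Follow-up. The windows are Week 16 (71, 141] and Week 24 (141, 211]. No document gives the interval from last dose to ETT, so 0 to 14 days is an assumption.

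- Week 16 is empty for L up to 71 (ETT on L) or 57 (ETT on L + 14).
- Week 24 is empty for L up to 141 or 127, respectively.
- Sweat chloride is therefore less protected than ppFEV1. An ETT Visit 3 weeks or more after last dose replaces Safety Follow-up and would give a later sample.

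*PEx.* Without a Week 52 Visit, the analysis period ends at the earlier of Day 365 and completion of study participation (SAP 8.1). Under Protocol 9.1.7, completion is the latest completed visit. Unobserved days = 365 − (L + 28), each ±7:

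- L = 57: 280 days (77% of 365)
- L = 85: 252 days (69%)
- L = 113: 224 days (61%)
- L = 169: 168 days (46%)

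**The case against.** The strongest reply is that the governing text already settles the matter. Four consistent statements keep Treatment Period subjects in follow-up, and against them 10.6 is one loose and discretionary phrase. Protocol 13.1.1.2 is similarly loose about discontinuation from the study. This stands as far as it goes: the follow-up rule is clear and sound, and the fault is an internal inconsistency rather than a flawed design. It does not remove the problem, because 10.6 is the only section that names dosing noncompliance and it does not point to the other rules.

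Other points that stand:

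- Section 9.9 names noncompliance with study procedures, not with dosing. The conflict for dosing rests mainly on 9.1.3, 9.1.5.2 and footnote c, which apply to anyone who stops drug early for any reason.
- Section 10 counts Run-in ELX/TEZ/IVA as study drug, so 10.6 also covers the Run-in Period. There, ending participation is essentially what 9.1.5.1 provides. The inconsistency is confined to the Treatment Period.
- SAP 8.2.1 tabulates treatment and study discontinuation with reasons by arm and lists the subjects, so such removals would be visible.
- The day limits are illustrative. Section 9.1.5 ties the ETT Visit to the decision to stop, and in a poor adherer that may come well after the last dose. Continued noncompliance despite education also makes very early removal the least likely case.
- PEx is outside the multiplicity-controlled tests and is reported as a rate. Shorter follow-up loses information, but no bias is shown.

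A reader might infer that removal is mandatory, or that every removed subject loses both the Week 16 and Week 24 ppFEV1 values. The documents support neither. The wording of 10.6 is permissive, and the ETT and Safety Follow-up spirometry can fill those windows.

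**Conclusion.** The point holds as a minor inconsistency in the Treatment Period. A site acting on 10.6 could stop visits for a consenting subject and so lose values that the analyses would use. For ppFEV1 the exposure is the Week 24 value after a fairly early removal, and both values only after a very early one. Sweat chloride is somewhat more exposed, and the remaining PEx follow-up is not recovered.

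The effect on the result is probably small, and its size is unknown because no removal rate is given. If removals are balanced between the blinded arms, the effect on the treatment difference is near zero. A reader might infer that the primary comparison is biased or underpowered. The documents give no basis for a bias estimate, and primary power stays above 90% even at an assumed 20% loss.

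The per-subject limits assume visits on target days, Safety Follow-up within its protocol window and, for sweat chloride, the assumed ETT timing. The textual conflict needs none of these assumptions.

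**What to change.** Replace the end of the last sentence of Protocol 10.6 so that it reads:

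> the investigator should consider discontinuing study drug treatment. Subjects who discontinue during the Treatment Period continue all scheduled study visits per Sections 9.1.5.2 and 9.9 unless consent or assent is withdrawn; subjects who discontinue during the Run-in Period follow Section 9.1.5.1.

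The split by period is needed because an unrestricted instruction to continue all visits would contradict 9.1.5.1.

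The cost is a short wording amendment and already scheduled visits for a few more subjects; the documents do not price those visits. No new procedure is added. If an amendment is impractical, a reminder to sites would achieve most of the benefit.

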## **10.7 Blinding and Unblinding**

This is a double-blind study.

### **10.7.1 Blinding**

All subjects (and their parents/caregivers/companions), site personnel (including the investigator, the site monitor, and the study team), and members of the Vertex study team will be blinded to the treatment codes.

Individuals who may be unblinded include only the following:

- Any site personnel for whom this information is important to ensure the safety of the subject in the event of a life-threatening medical emergency
- Any site personnel for whom this information is important to ensure the safety of the subject and her fetus in the event of a pregnancy
- Vertex Global Patient Safety (GPS) and Regulatory Affairs personnel to satisfy SAE processing and reporting regulations
- Vendor preparing the final (production) randomization list
- Vertex IWRS Manager
- Vertex Clinical Supply Chain
- DMC
- Vendor preparing the unblinded analysis of safety data for review by the DMC
- Analysts or vendor for modeling and simulations performing population PK modeling in preparation for regulatory submission(s)
- Bioanalytical contract research organization (CRO) analyzing PK samples and the Vertex Bioanalytical personnel who is not a member of the study team but reviews raw data from the Bioanalytical CRO. The Vertex Bioanalytical study team member will continue to be blinded.

### Access to Spirometry and SwCl Results:

During the conduct of the study, the Vertex study team will not have access to the spirometry or SwCl results after the first dose of study drug on Day 1 of the Treatment Period, with the exception of spirometry related to adverse event reporting.

Shortly before any planned efficacy analysis is conducted, the spirometry and SwCl data will be reviewed for data cleaning purposes by a limited Vertex team that does not have access to the treatment codes.

Individual SwCl test results will not be disclosed to the study sites with the exception of the Screening Visit and Day -14 values. Subjects and their parents/caregivers/companions should not be informed of study-related spirometry results until Vertex has determined that the study has completed (i.e., clinical study report [CSR] finalization), regardless of whether the subject has prematurely discontinued treatment.

